RESEARCH QUESTION AND OBJECTIVES	
The aim of the DUS is to address the following research question: Is there a difference in physicians' prescribing and monitoring practice in the periods before and after the update of the pregnancy prevention programme (PPP) for the oral retinoids acitretin, alitretinoin, and isotretinoin when treating women of childbearing potential?
 
Primary objective:
 
To evaluate the changes in the prescribing and monitoring practices following the update of the PPP in females of childbearing potential receiving prescriptions of the oral retinoids acitretin, alitretinoin, or isotretinoin by comparing the following key elements of the PPP between the pre- and the post-implementation period:
 
 • Contraceptives* before, during, and after treatment with oral retinoids • Time interval between prescription dates for oral retinoids during treatment episode • Laboratory pregnancy tests – where available - before, during, and after treatment with oral retinoids 
* contraceptive methods that require prescription and which are, therefore, captured in the administrative databases
 
Secondary objectives:
 
 • To describe the patient profile during the pre-and the post-implementation period, with respect to: 
 ○ Patient age ○ Indication for oral retinoids • To describe the prescriber specialty during the pre-and the post-implementation period • To describe the exposure characteristics during the pre-and the post-implementation period, with respect to: 
 ○ Active substance ○ Dose ○ Treatment duration • To describe the incidence of pregnancies exposed to oral retinoids during the pre- and the post-implementation period

	
 • To stratify the key elements of the PPP described in the primary objective by oral retinoid substance • To describe trends in the physician’s prescribing and monitoring practice of oral retinoids with respect to measures of the PPP (contraceptive use and performance of pregnancy tests) over the entire duration the study
COUNTRY(-IES) OF STUDY	The study will be conducted in France, Germany, Spain, and Sweden
AUTHOR	
[REDACTED]
 
[REDACTED]
 
On behalf of the oral retinoids consortium

MAH	marketing authorisation holder
PAS	post-authorisation study
PASS	post-authorisation safety study
PPP	pregnancy prevention programme
PRAC	Pharmacovigilance Risk Assessment Committee
RMM	risk minimisation measure
RWES	Real World Evidence Solutions
SAP	statistical analysis plan
SHI	statutory health insurance
SIDIAP	Sistema d'Informació per al Desenvolupament de l'Investigació en Atenció Primària
SmPC	summary of product characteristics
SNIIRAM	Système National d'Information Inter-Régimes de l'Assurance Maladie
STROBE	STrengthening the Reporting of OBServational studies in Epidemiology

1. TITLE

Evaluation of the effectiveness of pregnancy prevention programme (PPP) for oral retinoids (acitretin, alitretinoin, and isotretinoin): a European before-after drug utilization study (DUS) using secondary data

4. ABSTRACT

Full Study Title: Evaluation of the effectiveness of PPP for oral retinoids (acitretin, alitretinoin, and isotretinoin): a European before-after drug utilization study (DUS) using secondary data

Protocol version 3.0 dated 06 August 2019

Rationale and background:

Retinoic acid analogues comprise of a group of active substances known as the retinoids and are available as topical and oral preparations. Therapeutic indications include the treatment of severe acne (such as nodular or conglobate acne) resistant to adequate courses of standard therapy, hand eczema resistant to empirical treatment measures, and severe forms of psoriasis and other skin conditions. Therapy with systemic retinoids is associated with teratogenicity. Therefore, women who are pregnant or are planning a pregnancy must not be prescribed retinoids. Strict prescription guidelines and a PPP comprising education material for patients, physicians, and pharmacists as well as strict prescription guidelines have been put in place but exposure during pregnancy still occurs.

In January 2016, a Pharmacovigilance Risk Assessment Committee (PRAC) review noted that there are concerns about how well the requirements of the PPP are followed in clinical practice. In July 2016, the PRAC initiated an article 31 referral to assess the effectiveness of risk minimisation in relation to the PPP. After completion of the review in March 2018, the European Medicines Agency (EMA) confirmed that an update of measures of the PPP for the oral retinoids acitretin, alitretinoin and isotretinoin is needed. They, therefore, mandated the conduct of a DUS (category 1) to assess the effectiveness of these updated risk minimisation measures (RMMs). In June 2018, the decision to strengthen the recommendations for pregnancy prevention for oral retinoids was issued by the European Commission (EC).

Research question and objectives:

The aim of the DUS is to address the following research question: Is there a difference in physicians' prescribing and monitoring practice in the periods before and after the update of the pregnancy prevention programme (PPP) for the oral retinoids acitretin, alitretinoin, and isotretinoin when treating women of childbearing potential?

Primary objective:

To evaluate the changes in the prescribing and monitoring practices following the update of the PPP in females of childbearing potential receiving prescriptions of the oral retinoids acitretin, alitretinoin, or isotretinoin by comparing the following key elements of the PPP between the pre- and the post-implementation period:

- Contraceptives* before, during, and after treatment with oral retinoids
- Time interval between prescription dates for oral retinoids during treatment episode
- Laboratory pregnancy tests – where available - before, during, and after treatment with oral retinoids

* contraceptive methods that require prescription and which are, therefore, captured in the administrative databases

Secondary objectives:

- To describe the patient profile during the pre-and the post-implementation period, with respect to:
 - Patient age
 - Indication for oral retinoids
- To describe the prescriber specialty during the pre-and the post-implementation period
- To describe the exposure characteristics during the pre-and the post-implementation period, with respect to:
 - Active substance
 - Dose
 - Treatment duration
- To describe the incidence of pregnancies exposed to oral retinoids during the pre- and the post-implementation period
- To stratify the key elements of the PPP described in the primary objective by oral retinoid substance
- To describe trends in the physician's prescribing and monitoring practice of oral retinoids with respect to measures of the PPP (contraceptive use and performance of pregnancy tests) over the entire duration the study

Study design:

This is a multicountry, multisource, observational cohort study in females of childbearing potential receiving oral retinoids (i.e., acitretin, alitretinoin and isotretinoin) using a pre-post design. This study will cover time periods before and after the implementation of the updated RMMs related to the PPP update. The study will be based on secondary use of data extracted from established longitudinal healthcare databases (claims, primary care database, national registries). The pre-implementation period consists of 2 distinct phases, a 2-year phase (07/2014 to 06/2016) prior to the start of the referral in July 2016 and a 2.5-year phase between the start of the referral and the distribution of EM for the updated PPP in Q4 2018. The post-implementation period captures the 2-year phase after the distribution of the EM (01/2019 to 12/2020).

Population:

The study population will consist of females of childbearing potential (13-49 years of age, inclusive) receiving oral retinoids (i.e., acitretin, alitretinoin and isotretinoin) in the outpatient setting (at office-based practices and outpatient departments at hospitals), during the pre-defined periods identified from the selected data sources in the European target countries (i.e., France, Germany, Spain, and Sweden).

Inclusion criteria

- Female gender
- Childbearing potential (13-49 years of age, inclusive)
- Received or prescribed at least one prescription of the oral retinoids acitretin, alitretinoin, or isotretinoin in either the pre-implementation or post-implementation period

Exclusion criteria

All females in the age group 13 to 49 years with available information that they are not of childbearing potential before initiation of oral retinoids (such as records of hysterectomy or sterilisation) will be excluded.

Data for the oral retinoids acitretin, alitretinoin, and isotretinoin will only be extracted from databases in target countries where the respective active substance has been granted market authorisation.

No further exclusion criteria will be applied.

Variables:

The exposure is defined as one or more prescriptions of oral retinoids (i.e., acitretin, alitretinoin, or isotretinoin) during one of the study periods. The following variables will be considered (if available): patient age, oral retinoid prescribing and monitoring practice such as indication, length of prescription, treatment duration, and prescriber speciality, as well as PPP-specific variables such as prescriptions of contraceptive and – if available - laboratory pregnancy testing (before, during, and after treatment). In addition, information on exposed pregnancies and outcomes (if available) will be provided.

Data Sources:

The following established longitudinal data sources will be utilised for data extraction:

Claims databases

- France: System National d'Information Inter-Régimes de l'Assurance Maladie (SNIIRAM) of the Système National des Données de Santé (SNDS)
- Germany: Collective of insurants from company health insurance funds

Primary care database

- Spain: Sistema d'Informació per al Desenvolupament de l'Investigació en Atenció Primària (SIDIAP)

National health registers

- Sweden: national drug-, patient-, and birth registers

Study size:

All females of childbearing potential receiving oral retinoids (i.e. acitretin, alitretinoin, isotretinoin) available in pre-defined periods of the selected databases will be included in the analysis.

The number of females of childbearing potential receiving oral retinoids was checked for a 3-year period (2015-2017) in Germany, Spain, and Sweden. The number of patients is approximately 3,700 in Germany, 4,800 in Spain, and 20,500 in Sweden.

In France, only the number of boxes that was reimbursed in France in total (without any restriction to age and gender) is available without receiving ethical approval for the study, the number of approximately 1,041,000 boxes in one year suggests that the number of female patients of childbearing potential receiving oral retinoids will be sufficient for analysis.

Data analysis:

Given the study objectives, the analyses will mainly be descriptive and will be conducted by country and study time periods (both pre-implementation periods and post-implementation period). Some comparisons will be made especially between the different study time periods.

The analyses will be provided for the overall class of oral retinoids (acitretin, alitretinoin and isotretinoin) and for the single active substances.

A meta-analytic approach will be used to pool the results of the primary outcomes from the four databases and present the results by active substance for all study countries.

Results for key variables will be presented over time where patient numbers permit to provide insights on continuous trends capturing pre- and post-implementation periods.

In addition, an interrupted time series (ITS) analysis using segmented regression to identify ongoing trends in the study's primary outcomes will be considered in case the conditions for this analysis will be met.

Milestones

Anticipated start of data extraction: 2021

Registration in the EU-Post-authorisation study (PAS) register: after approval of protocol

Final report of study results: 2022

5. AMENDMENTS AND UPDATES

None

6. MILESTONES

The planned dates for key study milestones are:

Milestone	Planned date
Start of data extraction	July 2021
End of data extraction	January 2022
Registration in the EU-PAS register	After approval of protocol
Final report of study results	December 2022

7. RATIONALE AND BACKGROUND

7.1 Background

Retinoic acid analogues comprise of a group of active substances known as the retinoids and are available as topical and oral preparations. Therapeutic indications include the treatment of severe acne (such as nodular or conglobate acne) resistant to adequate courses of standard therapy, hand eczema resistant to empirical treatment measures, and severe forms of psoriasis and other skin conditions. Due to their anticarcinogenic activity retinoids are also used to treat certain types of cancers.

Therapy with systemic retinoids is associated with both acute and chronic toxicities as well as teratogenicity. Therefore, women who are pregnant or are planning a pregnancy must not be prescribed oral retinoids. A PPP comprising education material for patients, physicians, and pharmacists as well as strict prescription guidelines have been put in place, but exposure during pregnancy still occurs. A dedicated effort by women and their clinicians is required, involving patient selection, education and informed consent, detailed contraceptive counselling, and careful monitoring and management, including pregnancy testing before commencement, during, and after the end of therapy.

In July 2016, the PRAC initiated an article 31 referral to assess the effectiveness of risk minimisation in relation to the PPP. As stated in the article 31 referral, ‘Pregnancy is an absolute contraindication in the summary of product characteristics (SmPCs) for all oral retinoids in the EU’. A referral in 2003 for isotretinoin only, led to introduction of the isotretinoin PPP in the European Union (EU). Since the introduction of the PPP for isotretinoin, similar programmes have been introduced for the other retinoids used to treat dermatological conditions. The effectiveness of these PPPs has been kept under close review and although a reduction in the number of pregnancies exposed to these retinoids has been observed, cases of pregnancies exposed to retinoids as fore mentioned continue to occur.

In March 2018, the European Medicines Agency (EMA) completed its review of retinoid medicines and confirmed that an update of measures for pregnancy prevention is needed.

Based on 21 June 2018 EMA/261767/2018 the pregnancy prevention programme for acitretin, alitretinoin and isotretinoin includes:

- pregnancy tests before, during and after stopping treatment;
- the need to use at least one effective method of contraception during and after treatment;
- an ‘acknowledgement form’ to confirm that appropriate advice has been given to patients;

- a ‘patient reminder card’ stating that the medicine must not be used during pregnancy and including information about pregnancy testing and the need to use effective contraception.

The PPP addresses the issues of effective contraceptive use, pregnancy testing, and rigorous monitoring to the treating physician (i.e., dermatologist or GP in some countries after first prescription). In fact, the difference between the implemented PPP before and after the implementation of the updated RMMs is relatively small (see Table 1). The measures of the of the PPP are similar in the countries of interest for this study.

The updated RMMs include updated educational material (EM), in some countries patient reminder card and pictogram on the outer package, and in addition, the redistribution of direct healthcare professional communication (DHPC).

Differences in the set of implemented tools may exist between countries due to the requirements of local authorities.

Table 1 Measures of the PPP before and after the newly implemented, updated RMMs

Active substance	PPP	Contraception			Pregnancy test			Days' supply/Length of prescription
		Before	During	After	Before	During	After	
Acitretin	Old ¹	Yes	Yes	3yrs	Yes	Monthly	3yrs	Limited to 30d
	New ²	1mo	Yes	3yrs	Yes	Ideally monthly	3yrs	Ideally limited to 30d
Alitretinoin	Old ¹	1mo	Yes	Yes	Yes	Monthly	5wks	Limited to 30d
	New ²	1mo	Yes	1mo	Yes	Ideally monthly	1mo	Ideally limited to 30d
Isotretinoin	Old ¹	1mo	Yes	1mo	Yes	Monthly	5wks	Limited to 30d
	New ²	1mo	Yes	1mo	Yes	Ideally monthly	1mo	Ideally limited to 30d

d: day(s); mo(s): month(s); yr(s): year(s)

¹ Summary of product characteristics for acitretin, alitretinoin, and isotretinoin in countries of interest (i.e., France, Germany, Spain, and Sweden); for the time period 2012-2017

² Annex to the Amendments to relevant sections of the Product Information from 22 March 2018

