8. RESEARCH QUESTION AND OBJECTIVES

The aim of the DUS is to address the following research question: Is there a difference in physicians' prescribing and monitoring practice in the periods before and after the update of the pregnancy prevention programme (PPP) for the oral retinoids acitretin, alitretinoin, and isotretinoin when treating women of childbearing potential?

The objectives of the DUS are:

Primary objective:

To evaluate the changes in the prescribing and monitoring practices following the update of the PPP in females of childbearing potential receiving prescriptions of the oral retinoids acitretin, alitretinoin, or isotretinoin by comparing the following key elements of the PPP between the pre- and the post-implementation period:

- Contraceptives* before, during, and after treatment with oral retinoids
- Time interval between prescription dates for oral retinoids during treatment episode
- Laboratory pregnancy tests – where available - before, during, and after treatment with oral retinoids

* contraceptive methods that require prescription and which are, therefore, captured in the administrative databases

Secondary objectives:

- To describe the patient profile during the pre-and the post-implementation period, with respect to:
 - Patient age
 - Indication for oral retinoids
- To describe the prescriber specialty during the pre-and the post-implementation period
- To describe the exposure characteristics during the pre-and the post-implementation period, with respect to:
 - Active substance
 - Dose
 - Treatment duration
- To describe the incidence of pregnancies exposed to oral retinoids during the pre-and the post-implementation period
- To stratify the key elements of the PPP described in the primary objective by oral retinoid substance
- To describe trends in the physician's prescribing and monitoring practice of oral retinoids with respect to measures of the PPP (contraceptive use and performance of pregnancy tests) over the entire duration the study

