9. RESEARCH METHODS

9.1 Study Design

This is a multicounty, multisource, observational cohort study in females of childbearing potential receiving oral retinoids (i.e., acitretin, alitretinoin and isotretinoin) using established data sources in different European countries (i.e., France, Germany, Spain, and Sweden)

The study will employ a pre-post design to evaluate the effectiveness of the implementation of the updated RMMs with respect to the PPP according to the following schedule:

- Pre-implementation period: period prior to the date of the implementation of the updated RMMs
- Post-implementation period: period after the implementation of the updated RMMs

Periods will be defined as (also see Figure 1):

Pre-implementation period: The period before the implementation of the updated RMMs. The RMM tools will be distributed in the fourth quarter 2018 (the exact date may vary depending on the country). The pre-implementation period captures two periods:

- Pre-referral: the 2-year period before referral start in July 2016. This period will be used for the before and after comparison with the post-implementation period.
- Post-referral: the 2.5-year period between the referral start date in July 2016 and the distribution of the RMM tools in the target countries (assumed until December 2018). The duration of this period may vary depending on the duration of the approval and the distribution of the RMM tools in each country.

Post-implementation period: This period captures the time starting after the distribution of EM until December 2020. The start date of the period in each country will depend on the date on which the EM is approved by the respective national competent authorities.

The final dates of the study periods depend on the final schedule of the implementation of the updated RMMs in each country.

Figure 1: Overview of study periods

A single database for all target countries is not available. Therefore, a study approach was chosen which includes multiple data sources to gather drug utilisation data for oral retinoids (acitretin, alitretinoin and isotretinoin) in the European countries of interest.

Databases with longitudinal secondary patient data collected continuously over time will be used preferably to provide the most comprehensive data for the outcomes of interest.

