9.7.1 General Considerations

Given the study objectives the analyses will be mainly descriptive and will be conducted by country, by active substance and study time periods (both pre-implementation periods and post-implementation period). To allow for analysis across all data sources used in the study, a meta-analytic approach will be used to assess and pool the results from the four study countries together for each active substance (see 9.7.3.4).

The analyses will be provided for the overall class of oral retinoids and for the single active substances. Categorical variables will be presented as counts (n), proportions (%) with CI where relevant as for parameters used to address the primary objective and for the comparison of the incidence of exposed pregnancies. Continuous variables will be presented as means with standard deviation (SD) and as medians with interquartile range (IQR), where appropriate.

Changes in the reimbursement policy for contraceptives in the healthcare systems of the study countries will be considered to discard any differential misclassification of exposure.

The statistical unit will be the oral retinoid treatment episode and patient as well as prescription where appropriate. Patients who have multiple treatment episodes of oral retinoid use will be entered the cohort for analysis more than once.

The term “use” in the context of the analysis refers to the prescription or dispensing of drugs or IUD.

In the analysis, prescriptions of patients will be followed from the exposure start date to censoring date, i.e., transfer out of the database incl. death or the end of the study period, whichever comes first.

Statistical analyses will follow the tables shells validated by the MAH consortium and will be displayed using tables, listings and/or graphs. The statistical analysis will be conducted using SAS or an equivalent statistical analysis software. A detailed statistical analysis plan (SAP) will be prepared prior to data extraction.

The statistical results of all target countries and all active substances will be presented in a single report.

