9.7.3.2 Exposure

The following variables of exposure will be analysed:

Prescription length

The length of prescription will be determined by the date of prescription (or prescription fill/dispensing) plus the expected number of days of supply based on the days' supply reported with this prescription or, when not available, pack size and the recommended daily dose by the physician (if available) or, by default, according to the information of strength connected with the prescription and SmPC. The length will be provided in days.

The following analyses will be performed:

- Average length of prescriptions per treatment episode
- Overall number of prescriptions per patient

Duration of treatment

The duration of treatment will be analysed through the recorded prescriptions in the databases. The date of the first prescription issued (or filled) will be considered as treatment start date. End of treatment duration will be defined by the date of the last prescription plus the number of days' supply of this last prescription. Consecutive prescriptions of oral retinoids will be considered as one treatment episode (allowed gaps between prescriptions will be provided in the statistical analysis plan). The duration of treatment episodes will be provided in days.

The following analyses will be performed:

- Duration of treatment episodes
- Number of prescriptions per treatment episode
- Number of treatment episodes per patient

Average daily dose

The average daily dose will be analysed over a treatment episode based on dosage strength, pack size or day supply and number of prescriptions per episode.

9.7.3.3 *Pregnancy and pregnancy outcomes*

The following analyses will be performed for the pre-implementation and the post-implementation periods:

- Number of pregnancies exposed to oral retinoids
- Incidence rate of pregnancies exposed to oral retinoids
- Information on pregnancy outcome (i.e., live births, termination, stillbirth, miscarriage, or recorded birth defect) will be provided when available in the databases

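### Exposed-pregnancy incidence is compared between periods centred 4.5 years apart with no time term and is not named in any trend analysis, so a background decline, if one continued, could be read as an effect of the update

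*Protocol*

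**What the plan says.** Section 7.1 describes the history of the pregnancy prevention programmes, which began for isotretinoin after a 2003 referral and followed for the other retinoids. It reports that "although a reduction in the number of pregnancies exposed to these retinoids has been observed", and adds that exposed pregnancies still occur.

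Section 8 makes exposed pregnancies a secondary, descriptive objective: "To describe the incidence of pregnancies exposed to oral retinoids during the pre-and the post-implementation period". Section 9.7.3.3 lists the number of exposed pregnancies and the "Incidence rate of pregnancies exposed to oral retinoids", for the pre- and post-implementation periods. Section 9.7.1 promises confidence intervals "for parameters used to address the primary objective and for the comparison of the incidence of exposed pregnancies". It names no effect measure, model or adjustment for that comparison.

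The abstract (section 4) dates the pre-referral phase as "a 2-year phase (07/2014 to 06/2016) prior to the start of the referral in July 2016" and the post-implementation period as 01/2019 to 12/2020. Section 9.1 says of the pre-referral phase: "This period will be used for the before and after comparison with the post-implementation period". The 2.5-year post-referral phase between them is reported but is not the comparator.

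The trend objective in section 8 concerns prescribing and monitoring "with respect to measures of the PPP (contraceptive use and performance of pregnancy tests) over the entire duration the study". The abstract ties the interrupted time series to the primary outcomes. The four parameters listed in section 9.7.3.5 are two on contraception and two on pregnancy testing.

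**The concern.** Section 9.7.3.5 gives the interrupted time series a clear purpose: to tell an effect of the intervention from a trend already under way. The protocol thus recognises the weakness of a simple before-after contrast. It does not extend the remedy to exposed pregnancies, the outcome closest to harm and the only one for which its own background mentions an earlier fall.

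Section 7.1 calls the difference between the old and updated programmes relatively small, so a modest background trend could be as large as any real effect. The limitations in section 9.9.2 do not mention a secular trend. The checklist in Annex 2 answers No on methods for adjusting for confounding (item 10.4) and on discussing residual confounding (item 12.1.3). In a study commissioned to assess effectiveness, a lower rate after the update, shown with confidence intervals, will tend to be read as an effect.

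**Working it through.** **The plan's own figure.** The protocol gives no event count, precision or power for exposed pregnancies. Its only sample-size figure concerns proportions: 1.96² × 0.5 × 0.5 / 0.05² = 384.2, rounded up to 385, as in Table 4. It has no bearing on this outcome.

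**Distance between periods** (dates from section 4; comparator from section 9.1).
- Pre-referral, 07/2014 to 06/2016: midpoint 1 July 2015.
- Post-referral, 07/2016 to 12/2018: midpoint 1 October 2017.
- Post-implementation, 01/2019 to 12/2020: midpoint 1 January 2020.

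The compared periods are 4.5 years apart from midpoint to midpoint, with 2.5 years between the end of one and the start of the other. The three midpoints are evenly spaced at 2.25 years.

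**Rate ratio from a background decline alone.** The documents give no rate of decline, so the annual fall r is assumed. With no effect of the update, rate ratio = (1 − r)^4.5:
- r = 3%: 0.97^4.5 = 0.87
- r = 5%: 0.95^4.5 = 0.79
- r = 10%: 0.90^4.5 = 0.62

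Against the whole 54-month pre-implementation period (midpoints 3.25 years apart), (1 − r)^3.25 gives 0.91, 0.85 and 0.71.

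**How often a 95% interval would exclude 1.** Assume Poisson counts, equal person-time, and standard error of the log ratio √(1/d₁ + 1/d₂), with d₁ and d₂ the pre and post event counts. The counts are also assumed. At r = 5%, log 0.794 = −0.231.
- d₁ = 100, d₂ = 79: SE = 0.150, z = 1.54, chance about 34%.
- d₁ = 400, d₂ = 318: SE = 0.075, z = 3.07, chance about 87%.

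**Cost of adjusting for a linear trend.** Take 13 half-years (9 before the update, 4 after) with equal information in each, and measure the standard error in units of one half-year's.
- Unadjusted, 4 pre-referral against 4 post half-years: √(1/4 + 1/4) = 0.707.
- Linear time plus a post-implementation step, all 13 half-years: the step's sum of squares is 4 × 9/13 = 2.769. The part shared with time is 18²/182 = 1.780, which leaves 0.989. SE = 1/√0.989 = 1.006, and 1.006/0.707 = 1.42.
- Same, with a separate indicator for the post-referral phase: the slope then comes only from within the three periods (sum of squares 5 + 10 + 5 = 20). SE = √(0.5 + 9²/20) = 2.13, and 2.13/0.707 = 3.0.
- Same, with the post-referral phase excluded: sum of squares 5 + 5 = 10. SE = √(0.5 + 9²/10) = 2.93, and 2.93/0.707 = 4.1.

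The factor of 1.4 therefore holds only when the post-referral phase counts as ordinary background. Separating or dropping that phase costs much more, which is why those variants belong in a sensitivity analysis.

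**The case against.** The best defence has five parts.

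- **The background statement is thin.** Section 7.1 reports a fall in number, not rate, without dates, since programmes that go back to the 2003 referral. An early drop followed by a plateau through 2014 to 2018 fits it equally well, and counts can fall because fewer women are treated. This stands. A reader might infer that the protocol shows exposed pregnancies falling during the study years, or that it contradicts a flat background. It does neither.
- **No crude rate ratio is specified.** The objective is to describe, the analyses are mainly descriptive, and checklist item 3.4 marks measures of association as not applicable. This also stands. Section 9.7.1 nevertheless announces a comparison of incidence with confidence intervals, and section 9.1 fixes which periods are compared.
- **Three periods are reported, not two.** Section 9.7.1 has results for both pre-implementation phases, so a steady fall should be visible before the update. This is a real partial safeguard. The designated contrast does not use the third point, and no rule says how it bears on the interpretation.
- **The abstract promises key variables over time.** They are undefined and could include pregnancies. It would be too strong to say that pregnancies are left out of every trend analysis; they are left out of those whose content the protocol names.
- **Detail belongs in the statistical analysis plan.** The choice of model does. The objectives, the comparator and the scope of the time series are set in the protocol, and section 9.7.3.5 makes the final choice of parameters depend on results for the primary outcomes, which points away from pregnancies.

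**Conclusion.** The point holds in a conditional form. The protocol compares exposed-pregnancy incidence across midpoints 4.5 years apart with no stated time term, and its named trend analyses cover only contraception and pregnancy tests. If a background decline continued, part or all of the contrast could be mistaken for an effect of the update: a rate ratio of 0.87, 0.79 or 0.62 for an assumed steady fall of 3%, 5% or 10% a year. Both the continuation of the fall and its size are assumptions.

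The documents do not support saying that such a bias is present. They support saying that the plan commits to nothing that would reveal or correct it beyond one intermediate rate. Because the outcome is secondary and descriptive, the risk lies in interpretation and not in a formal primary test. It is worth fixing before data extraction.

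**What to change.** In section 9.7.3.3, report exposed-pregnancy incidence with confidence intervals by year or half-year over 07/2014 to 12/2020 in each country. In section 8, add exposed pregnancies to the trend objective.

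Where event counts allow, fit a Poisson or negative binomial model with calendar time, a post-implementation indicator and a log person-time offset. Whether they allow should be judged from the data and not presumed for named countries: the protocol has no pregnancy counts, and early losses are incompletely captured in Sweden (section 9.4.3.1). Show the trend-adjusted rate ratio with its 95% interval beside the unadjusted contrast. In a sensitivity analysis, identify the post-referral phase separately or exclude it, so that change prompted by the referral is not simply absorbed into the trend. Where counts are too small, show the rates and state that the before-after contrast does not account for any background trend.

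The cost is some protocol and analysis-plan wording and one further model on data already to be extracted. The adjusted log ratio has a standard error about 1.4 times that of the pre-referral against post-implementation contrast under equal person-time, and about 3 to 4 times in the sensitivity variants. Those variants will be informative only where events are numerous. Showing both estimates side by side loses nothing.
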